10.2. SECONDARY EFFICACY ENDPOINTS AND ANALYSES

Change from baseline will be calculated for all secondary efficacy variables, namely:

Syneos Health #1009367

VIIS Scores:

- VIIS erythema score
- Central reader assessed VIIS scaling and erythema scores
 - Clinical Outcomes Assessments
- The EQ 5D 5L patient/caregiver overall assessment score
- The clinical global impression of severity scale, the patient/observer global impression scales
- The patient-/observer-reported scratching scales,
- The patient-/observer-reported burden of bathing/showering, the patient reported itching scale,
- The CDLQI/DLQI scales,
- Lipid biomarker measurements and TEWL (exploratory biomarkers).

[figure not shown]
It will be noted that in addition to an overall Visual Analog Scale (0 to 100) assessment that measures self-reported health, the EQ-5D-5L also evaluates, by category (no problem, slight problems, moderate problems, severe problems and extreme problems), the status of a subject in five domains (Mobility, Self-Care, Usual Activities, Pain/Discomfort and Anxiety/Depression). Guidance documentation for the use of the EQ-5D-5L specifically warns against the conceptualization of these categories as a mathematically meaningful 5-point scale, thus only the VAS scale (not individual domain categorical results) will be statistically evaluated.

The secondary efficacy variables are given in section 6, with further detail of each score given in Table 10.2.1 below. The schedule of assessments is given in Section 4 and each individual score is shown in Appendix 1-Outcome Scales.

[figure not shown]
Table 10.2.1: Description of secondary efficacy variables

Syneos Health #1009367

Syneos Health #1009367

Secondary Analysis

The secondary efficacy variables will be analyzed using one or more of the following analyses applied to the primary endpoint:

1. A MMRM generalized linear model applied to secondary efficacy variable change scores derived from observed values;

Syneos Health #1009367

- 2. A GEE model applied to secondary efficacy variable scales after dichotomization to reflect response (yes/no);
- 3. A linear model applied to secondary efficacy variable observed values after transformation to an AUC measurement;
- 4. A log rank analysis and a proportional hazards model applied to time to first response.

These analyses will be carried out in an analogous fashion as for the primary efficacy variable (see above for a description of each analysis applied to the primary efficacy variable).

As with the primary efficacy variable (VIIS scaling), the within-group change from baseline will be the primary focus of interest in the MMRM analysis. Because SLS patient symptoms do not spontaneously improve over time, the within-group comparison provides a clinically meaningful evaluation. The planned analyses for selected secondary efficacy endpoint are outlined in Table 10.2.2.

Table 10.2.2: Analyses of the Secondary Efficacy Variables

	Analyses			
Secondary Efficacy Variable	MMRM	RESPONDER ANALYSIS (Estimating Equation)	AUC (Linear Model)	Survival
VIIS Erythema (Investigator Assessment)	✓		√	✓
VIIS Scaling (Photographic Assessment by Central Reader)	✓	✓	✓	✓
VIIS Erythema (Photographic Assessment by Central Reader)	✓		√	√

¹The 100 mm VAS will be analyzed using MMRM. Categorical outcomes will be displayed in a contingency table (Treatment x Category) containing frequency and percent occurrence of categorical outcomes.

²The total score (i.e., sum of 0 - 3 rating on 10 individual questions) will be analyzed using MMRM for change scores and a linear model for AUC. Responses to individual questions will be provided in a listing.

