10. EFFICACY

Overview

All efficacy variables are initially captured on a continuous or semi-continuous scale. Observed values at the time of collection and change from baseline value at each time point will be summarized descriptively. Mixed Model Repeated Measures (MMRM) analysis will be carried out on change from baseline scores for the primary and secondary efficacy variables for reproxalap-treated subjects (not vehicle-treated subjects). Hereinafter, in this Statistical Analysis Plan, drug-treated shall mean reproxalap-treated. Additional analyses in drug-treated subjects will be performed on certain efficacy variables. Further details of the tests to be performed on each endpoint are given in Table 10.2.1 below. The specific additional analyses are described below.

- 1) The VIIS outcomes will be converted to a binary response variable (yes/no) defined as a 1-unit and 2-unit improvement from baseline. The probability of response in drug-treated subjects will be analyzed over time using generalized estimating equation (GEE) models.
- 2) Change from baseline over time will be converted into an Area Under the Curve (AUC) value using the trapezoidal rule. AUC for drug-treated subjects will be inferentially compared to zero (0 = no change from baseline) using a linear model.
- 3) Time to first response (1-unit improvement and 2-unit improvement) for the VIIS outcomes (scaling and erythema) will be evaluated using a Kaplan Meier survival curve for drug-treated subjects.

Tables will be generated for each endpoint presenting appropriate descriptive and inferential statistics to convey the results of the analyses. Tables will be augmented by figures for selected analyses.

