Along with the table detailing the results of the MMRM model, a consolidated table presenting the essential information for the primary analysis will be constructed. The primary endpoint will be deemed to have been met if the Visit 8 (week 24) term is significant, and the term coefficient is negative.

Secondary and Sensitivity Analyses Related to the Primary Outcome Variable

The following analyses will be performed to provide additional insight into VIIS scaling.

Responder Analysis

For drug-treated subjects, responder status will be assigned to a subject if at a given post treatment time point an improved change from baseline of at least 1 VIIS scaling

Syneos Health #1009367

unit occurs. A Generalized Estimating Equation (GEE) model will be used to evaluate the predicted log odds, odds and probability of response. The model will include the effect of visit (treated as a factor). An unstructured covariance structure will be assumed and a Type III model will be evaluated. If the unstructured covariance structure matrix results in a lack of convergence, then first-order autoregressive (AR1) and compound symmetric (CS) covariance structure will be used in that order.

Results will be captured in a consolidated table that contains the following information:

- Number and percent of observed responders and non-responders at all post-treatment time points;
- Significance levels for the visit effects;
- The model predicted log odds, odds and probability of response with standard errors and 95% confidence intervals for each visit;
- Within-group contrasts expressed as an odds ratio, accompanied by a 95% confidence interval.

AUC Analysis

For drug-treated subjects, AUC for change from baseline over all post-treatment time points will be calculated for each subject using the trapezoidal rule. A linear model comparing AUC to zero (no change from baseline) will be performed.

Survival Analysis

For drug-treated subjects, time to first response (i.e., a one-unit VIIS scaling improvement) will be captured in a Kaplan Meier plot. A hazard rate estimate will be generated.

Analysis for Patients Experiencing one or more Treatment interruptions

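### SAP 10.2 defines the secondary AUC on observed values, in conflict with the change-from-baseline AUC that the SAP uses elsewhere and tests against zero

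*SAP*

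**What the plan says.** Three places in the SAP describe an AUC analysis that bears on the secondary variables.

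- **Section 10, Overview item 2:** "Change from baseline over time will be converted into an Area Under the Curve (AUC) value using the trapezoidal rule", and then "AUC for drug-treated subjects will be inferentially compared to zero (0 = no change from baseline) using a linear model".
- **Section 10.1, AUC Analysis (primary variable):** "AUC for change from baseline over all post-treatment time points will be calculated for each subject using the trapezoidal rule", and "A linear model comparing AUC to zero (no change from baseline) will be performed".
- **Section 10.2, Secondary Analysis item 3:** "A linear model applied to secondary efficacy variable observed values after transformation to an AUC measurement". This item gives no null value.

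Item 1 of the same list in 10.2 does name change scores: "A MMRM generalized linear model applied to secondary efficacy variable change scores derived from observed values". The list is introduced by "The secondary efficacy variables will be analyzed using one or more of the following analyses applied to the primary endpoint" and followed by "These analyses will be carried out in an analogous fashion as for the primary efficacy variable", with a pointer back to the descriptions in 10.1.

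AUC is ticked in all three visible rows of Table 10.2.2: investigator erythema, central-reader scaling and central-reader erythema. Footnote 2 to that table adds an AUC for a total score of ten questions rated 0 to 3, without saying whether it uses observed or change scores.

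**The concern.** Zero is a sensible null for an AUC of change from baseline: a subject who does not change contributes an area of zero. It is not a sensible null for an AUC of raw severity scores. VIIS items run from 0 to 4 (SAP 10.1), so the area under observed scores cannot be negative, and it is positive for any subject with disease.

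Item 3 supplies the observed-score input. Sections 10 and 10.1 supply the only null in the SAP for an AUC test, and the sentence after the list in 10.2 carries the primary methods over. A programmer who takes the input from item 3 and the test from 10.1 would produce p-values that reflect baseline severity. SAP 8.2 offers significance levels as an index of change and applies no multiplicity adjustment, so such p-values would be reported as something they do not measure.

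**Working it through.** The documents give no figure for the AUC analysis, so there is none to reproduce. The check has three steps.

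**Inputs.**
- Treated subjects in Part 1: n = 6 (protocol synopsis, Statistical Analysis).
- VIIS range 0 to 4, and investigator-assessed baseline scaling of grade 2 or higher in the target area (SAP 10.1). The documents set no minimum for erythema.
- Times: weeks 0, 12, 20 and 24, taken from the primary model's Visits 1, 5, 7 and 8 (SAP 10.1).
- Assumptions: two-sided 5% level (the AUC items state none; protocol 10.1 uses it for the Part 2 sample size); an intercept-only linear model, which is a one-sample t-test; and all grade distributions.

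**Step 1: fixed example with no change.** Six subjects stay at grades 2, 2, 3, 3, 3, 4 for 24 weeks.
- Observed AUC per subject = 24 × grade: 48, 48, 72, 72, 72, 96.
- Mean = 408/6 = 68. The SD of the grades is √(2.833/5) = 0.753, so the SD of the AUC is 24 × 0.753 = 18.07.
- t = 68 / (18.07/√6) = 68/7.376 = 9.22 on 5 df, p = 0.0003.
- Every change AUC is exactly 0.

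A lower-scoring example, erythema fixed at 0, 1, 1, 2, 2, 3, gives a mean AUC of 36, t = 3.50, p = 0.017, again with no change in anyone.

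**Step 2: the same six subjects, all improving.** Each drops one grade by week 12 and stays there.
- Change AUC = −(12/2 + 8 + 4) = −18 for every subject.
- Observed AUC = 24 × baseline grade − 18, so the mean is 68 − 18 = 50 with the same SD, and t = 50/7.376 = 6.78.

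Improvement lowers the observed-score statistic, from 9.22 to 6.78. The test becomes less extreme as the drug works.

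**Step 3: rejection rates under no change.** These come from 100,000 simulated trials per case, with scores kept within 0 to 4, visit-to-visit noise, a trapezoidal AUC, and a t-test against 0 at n = 6.

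| Assumed scores | AUC of observed values | AUC of change |
|---|---|---|
| Integer scaling, baseline grades 2/3/4 at 30/50/20% | 100% | 3.4% |
| Integer erythema, grades 0 to 4 at 20/30/30/15/5% | 84% | 3.2% |
| Integer erythema, grades 0 to 3 at 50/30/15/5% | 41% | 2.9% |
| Continuous, mean 2 or 3, SD 0.6 | 100% | about 5% |
| Continuous, mean 2, SD 1.0 | 99% | about 5% |
| Continuous, mean 1, SD 0.7 to 1.0 | 74–93% | 4–5% |

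The integer rows add a one-grade error up or down, each with probability 15%, at every visit. The continuous rows use a within-subject SD of 0.35 to 0.50.

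**The case against.** The strongest reply is that the SAP, read as a whole, already answers the question. Zero appears as the AUC null only in sections 10 and 10.1, and in both it is tied to change from baseline. Section 10.2 opens by saying that change from baseline will be calculated for all secondary variables, presents its list as the primary-endpoint analyses, and closes by sending the reader back to 10.1. Exploratory item 6 in section 10.4 also refers to an AUC of change from baseline. Observed values in item 3 could simply name the unimputed source data, in keeping with SAP 8.5. And because improvement is a negative change (SAP 10.1), a positive observed-score AUC would point towards worsening and should look odd to anyone checking the output.

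Most of this stands. A reader might infer that the SAP prescribes a test that is significant even when nothing has changed. The documents do not support that: no passage pairs an observed-score AUC with a zero null, and the carry-over sentence points to the change-score version.

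The reply does not remove the conflict. Item 1 of the same list separates change scores from observed values, so the two terms are not interchangeable there. The list is also not a faithful summary of the primary methods: item 4 names a log rank analysis and a proportional hazards model, whereas 10.1 plans a Kaplan-Meier plot with a hazard rate estimate in drug-treated subjects. Different wording in item 3 therefore cannot safely be dismissed as shorthand.

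**Conclusion.** Item 3 is an incorrect specification that contradicts sections 10 and 10.1 and the carry-over sentence in 10.2. The change-score AUC is very likely what is meant, and under it the test behaves properly, with about 3% to 5% rejection under no change at n = 6.

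The harm is conditional on item 3's input being used with the zero null. In that case the rejection rate under no change is about 100% for scaling grades 2 to 4 and about 41% to 84% for integer erythema grades. The erythema range rests entirely on assumed distributions, since the documents give none, so false significance there is likely but not certain. The scaling figure assumes that central-reader baseline grades resemble the investigator's entry requirement of grade 2 or higher.

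The consequence is limited. This SAP covers Part 1 only (section 2), section 8.3 plans descriptive statistics for the secondary endpoints and reserves inference for the primary analysis, and protocol section 10 rests the efficacy claim on Part 2 alone. Section 10 of the SAP does, however, call for an inferential comparison of the AUC with zero, so these p-values would be produced. The primary repeated-measures analysis is unaffected.

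**What to change.** In SAP 10.2, Secondary Analysis item 3, replace the words observed values with change-from-baseline scores, leaving the rest of the sentence as it is. In footnote 2 of Table 10.2.2, state that the AUC is of change from baseline. The null of zero then fits every AUC test in the plan.

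The cost is a few words in the SAP. No data collection, sample size or primary analysis changes. The edit should be made before the Part 1 data are unblinded, so that the definition is settled in advance, and the corrected wording should be the one carried into any Part 2 plan.

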10.3. SUBGROUPS ANALYSIS

Subgroup analysis on age group

Syneos Health #1009367

To account for treatment differences between age ranges of subjects, analyses of efficacy and laboratory summary tables will be displayed by adult only (≥ 18 years), pediatric only (<18 years) and combined adult and pediatric.

Pending the final number of pediatric patients enrolled and distribution of age;
 additional analysis may be performed for patients ≤ 10 years of age and >10 to <
 18 years of age

10.4. EXPLORATORY ANALYSES

Efficacy Endpoint

Additional exploratory analysis maybe conducted on primary efficacy endpoint by sponsor. Exploratory analysis will be conducted for both targeted efficacy area and for combined regions as appropriate, such as but not limit to:

- 1) Repeat primary analysis MMRM model on drug-treatment patients to evaluate change from baseline for combined visits (Visit 5, Visit 7 and Visit 8)
- 2) Repeat primary analysis MMRM model on all treated patients (including both drug-treatment and vehicle-treated patients) to evaluate change from baseline for combined visits (Visit 5, Visit 7 and Visit 8) and each individual visit
- 3) all patients (including both drug-treatment and vehicle treated patients)
- 4) Responder analysis for patient with at least 2 units VIIS scaling improvement from baseline at any post treatment time point
- 5) Survival analysis for the time to first response defined as 2 units VIIS scaling improvement from baseline
- 6) AUC analysis for change from baseline of all VIIS regions combined
- Analyze change from baseline of VIIS total score at week 24 analysis using MMRM model
- 8) Contralateral analysis of between group contrast comparing VIIS scaling score change from baseline between treated area vs. untreated area
- 9) To further evaluate the impact of 'treatment interruption' on treatment effect, the same analysis approach used for primary analysis on primary endpoint may be repeated on following subgroups:
 - a. patient with 'treatment interruption' for at least 1 week

Syneos Health #1009367

b. patient without 'treatment interruption' or with 'treatment interruption' for less than 1 week

Biomarker Endpoint

Selected skin lipid bio markers, captured as the post-treatment value at Week 24 or at an early termination visit as the post-treatment minus baseline value (change score), may be correlated with various outcome symptom scales or functions of outcome symptom scales. Such skin lipid biomarkers are listed in Table 10.3.1.

Exploratory analyses will be performed on lipid biomarkers from skin cell analysis and TEWL using the following methodologies:

Analysis between biomarkers and outcome scales (investigator and central reader VIIS scaling and erythema) for time matched assessments will be performed using appropriate correlation procedures.

Table 10.3.1: Lipid Values Selected for correlational analysis (captured as post treatment values or change score values)

Table 10a. Lipid Values Selected for Correlational Analysis (Captured as Post Treatment Values or Change Score Values)

Abbreviation	Variable	
Total CER	Total Ceramides	
CE	Cholesterol Ester	
CHOL	Cholesterol	
CE/CE + CHOL	Ratio Cholesterol Ester/ Cholesterol Ester plus Cholesterol	
CHOL:CER	Ratio Cholesterol/Ceramide	
CER1 EOS	Omegahydroxysphingosine (aka. Ceramide 1)	
CER2 NS	NS: Nonhydroxysphingosine (aka. Ceramide 2)	
CER5 AS	Alphahydroxysphingosine (aka. Ceramide 5)	
EOS: tCER	Ratio Omegahydroxysphingosine/Total Ceramides	
tEO	Total omega-esterified ceramides	
EOS 68:3;2	Omegahydroxysphingosine subspecies with a 68-carbon total chain length, containing 3	
	double bonds and 2 hydroxyls	
EOS 70:3;2	Omegahydroxysphingosine subspecies with a 70-carbon total chain length, containing 3	
	double bonds and 2 hydroxyls	

Syneos Health #1009367

11. SAFETY OUTCOMES

All outputs for safety outcomes will be based on the SAF population.

The safety outcomes include dermatological endpoints, vital sign measurements, physical examinations, hematology and chemistry laboratory testing, ECG readings, use of concomitant medications, and incidence, severity and duration of adverse events and TEAEs.

Safety tables will be presented by treatment and overall.

Tables variously organized by preferred terms, system organ class, treatment emergence, treatment relationship, severity and study termination will be presented for AEs, TEAEs, unexpected AEs and SAEs.

Descriptive statistics will be presented by treatment and time for safety laboratory values or in change tables for categorized lab variables (e.g., normal vs. abnormal, present vs. absent). Other safety information (e.g., normality of dermatological endpoints, normality of vital signs, normality of physical examinations, normality of ECG outcomes, concomitant medication usage) will be summarized in tables and medically evaluated.

No inferential statistical testing is planned on the safety data, all data will be summarized and listed only. If any post-hoc inferential testing of any variable seems appropriate, the comparison will be made using an appropriate statistical test.

11.1. SAFETY NARRATIVES

Treatment and vehicle group safety narratives will be written. If required a safety narrative will be written for selected subjects.

11.2. ADVERSE EVENTS / ADVERSE DRUG REACTIONS

Adverse events (AEs) will be coded using a Medical Dictionary for regulatory Activities (MedDRA) version 20.0 or later preferred term (PT) and system organ classification (SOC).

Patients with multiple events within the same System Organ Class and/or same Preferred Term are only counted once within the respective frequencies.

All reported AEs (whether treatment emergent or not) will be included in by-patient AE listings. Sorting will be by patient, date of event, SOC, PT and then verbatim description.

Syneos Health #1009367

An AE will be considered treatment emergent (TEAE) if it begins or worsens in severity after the first dose of the double-blind Study Treatment through 28 days after the last dose of Study Treatment, or the date of initiation of another investigational agent or surgical intervention or rollover to the extension study, whichever occurs first. Partial AE start dates will be imputed as detailed in Section 8.5.

ALL AEs and TEAEs.

Incidence of AE and TEAEs will be presented by SOC and PT. The AE and TEAEs listings will include treatment group, the duration of the event, it severity and whether it was considered to be related to treatment. The listings will also include the number of days between first dose and event.

SOC and PT will be presented, where the severity per patient will be counted at each level of summarization. In addition, a summary of all TEAEs by relationship to Study Treatment (related, not related), SOC and PT will be presented, where the strongest relationship to Study Treatment per patient will be counted at each level of summarization.

SEVERITY.

Severity is classified as mild, moderate, severe or life-threatening.

Missing severity for TEAEs will be counted as 'Severe'.

RELATIONSHIP TO STUY MEDICATION.

Relationship, as indicated by the investigator, will be defined as definitely, possibly, unlikely or not related.

Adverse events with a missing relationship to study medication will be noted as "related" to study medication. If a patient reports the same AE more than once within the same SOC/PT, the AE with the strongest relationship to study medication will be used in the relationship summaries.

TEAEs LEADING TO STUDY DRUG DISCONTINUATION.

TEAEs leading to permanent discontinuation of study medication are those events that are marked as 'discontinued from study' under action taken with study medication in the adverse events page of the CRF.

For TEAEs leading to permanent discontinuation, a summary table with incidence rates (frequencies and percentages) by SOC and PT will be prepared.

Syneos Health #1009367

SERIOUS ADVERSE EVENTS.

Serious adverse events (SAEs) are those events recorded as a "serious Adverse Event (Y)" on the adverse events page of the CRF. A summary of serious TEAEs and Serious treatment related TEAEs by SOC and PT will be prepared.

ADVERSE EVENTS LEADING TO DEATH.

Adverse events leading to death are those events with 'Death' recorded under Outcome in the adverse events page of the CRF. A summary of TEAEs and SAEs leading to death by SOC and PT will be prepared. A listing of AEs leading to death will be included with the TEAEs flagged.

SUMMARY TABLES AND LISTINGS.

Summary tables will be based on treatment emergent adverse events (TEAEs). The incidence of TEAEs will be presented using counts and percentages of patients with TEAEs and tabulated by SOC and PT. SOC will be sorted in descending frequency and PT within SOC will be sorted by descending frequency based on the incidence across patients overall. If a patient has multiple occurrences (start and stop) of an event associated with a specific SOC or PT within a SOC, a patient will only be counted once in the incidence count for the SOC or PT within SOC respectively.

An overall summary table of AEs by treatment group will be presented detailing the number and percentage of patients, and number of events for the following categories:

- At least one AE
- At least one TEAE;
- Serious TEAEs;
- Treatment Related TEAEs;
- Treatment Related Serious TEAEs;
- TEAEs leading to Discontinuation from Study Treatment;
- TEAEs resulting in death;

The incidence of all TEAEs by SOC and PT will be presented for the following:

- All TEAEs;
- Serious TEAEs;
- Treatment Related TEAEs;
- Treatment Related Serious TEAEs;
- TEAEs leading to Discontinuation from Study Treatment;
- TEAEs resulting in death;

Treatment listings will include the treatment group, start and stop dates/times of the AE, and days on study relative to the day of first dose of Study Treatment.

Syneos Health #1009367

The following additional listings will be provided:

- Listing of deaths
- Listing of Serious TEAEs
- Listing of non-treatment-emergent SAEs
- Listing of TEAEs leading to withdrawal or temporary withdrawal of Study Treatment
- Listing of all AEs with a flag for TEAEs and onset (Prior = prior to first dose of double-blind medication, or Treatment = on or after first dose of double-blind medication.)

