3.5 Study Duration for Individual Subjects

Following the Screening Visit, eligible subjects will enter the study for up to 28 weeks in each Part 1 and Part 2. This comprises of a 24-week study treatment phase followed by a 4-week follow-up period.

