6.5 Adverse Events

AEs will be collected from the time the subject signs the informed consent form through 30 days after the last dose of study drug. AEs must be recorded in the subject's CRF. The Sponsor and Investigator or qualified study personnel will review and evaluate adverse events on an ongoing basis. See Section 9 for further detail on AE reporting.

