9 ADVERSE EVENT REPORTING

AEs will be collected from the time the subject signs the informed consent form through 30 days after the last study drug administration.

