9.1.2 Treatment-Emergent Adverse Events

A TEAE will be an AE that occurred during the study after the first dose of study drug or that was present prior to dosing and exacerbates after the first dose of study drug.

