8.4. KEY DEFINITIONS AND TERMINOLOGY

Reference start date and study day

Study Day will be calculated from the reference start date and will be used to show start/stop day of assessments and events.

Baseline Value

For purposes of analysis, the baseline value is defined as the last non-missing value obtained prior to initiation of study drug.

Change from Baseline.

Change from baseline for a given endpoint is defined as the difference between a post-treatment study day value and the baseline variable value and will be calculated directionally as post-study minus baseline.

Note that for the VIIS, it is planned that a single investigator will complete this instrument prior to randomization on day 1 of Part 1.

Day 1 (Baseline)

Day 1 is the earliest day that the study drug is first initiated.

Age

Syneos Health #1009367

Age is calculated as the number of whole years from a subject's date of birth to the date of informed consent.

Study Visit.

Study visit is the nominal visit as recorded on the eCRF.

Total Days on Study

Total days on study is defined as the number of days from Day 1 to the date of completion or early termination.

Last Dose of study drug

Last dose of study drug is defined as the number of days from day 1 to the date of last dose of study drug.

Duration of SLS.

The duration of SLS is defined as the number of whole years from the date of onset of SLS diagnosis to the date of informed consent.

Adverse Event

An adverse event is any untoward medical occurrence in a patient or clinical investigation patient, temporally associated with the use of a medicinal product, whether or not considered related to the medicinal product.

Treatment Period

The Treatment Period covers the duration that a patient is in the study from Baseline (Day 1) to Week 24.

Safety Follow-up Period

The Safety Follow-up Period continues for 28 days after the last dose of study treatment at Week 24 through Week 28.

Definition of Study Completion

A patient will be defined as "completed" if she or he completes the Week 24 study visit.

End of Study Definition

Syneos Health #1009367

End of study is defined as the date when the patient has completed one of the following: completed the follow-up visit after the Week 24 visit, permanently discontinued from the study, or lost to follow-up.

Day of Study Termination

Day of study termination = Termination Date - Date of Baseline (Day 1) + 1.

Percent Change from Baseline

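### The SAP's treatment-emergent window can close at a surgical procedure while the subject is still on study drug, and stops two days short of AE collection; neither departure from the protocol definition is declared

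*SAP*

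**What the plan says.** SAP Section 11.2 counts an adverse event as treatment-emergent when the event "begins or worsens in severity after the first dose of the double-blind Study Treatment through 28 days after the last dose of Study Treatment". It then adds earlier closing points: "the date of initiation of another investigational agent or surgical intervention or rollover to the extension study, whichever occurs first". The same section states "Summary tables will be based on treatment emergent adverse events (TEAEs", and lists incidence tables by system organ class and preferred term for all, serious, related, related serious, discontinuation and fatal TEAEs.

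Protocol Section 9.1.2 is wider: "A TEAE will be an AE that occurred during the study after the first dose of study drug". It also includes events present before dosing that get worse afterwards. It has no surgical, investigational-agent, rollover or 28-day limit.

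Collection runs longer than the SAP window. Protocol Section 9 says "AEs will be collected from the time the subject signs the informed consent form through 30 days after the last study drug administration", and Protocol Section 6.5 agrees. The SAP's 28 days match its own follow-up definition in Section 8.4: "The Safety Follow-up Period continues for 28 days after the last dose of study treatment at Week 24 through Week 28".

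SAP Section 2 says that its methods override those in the protocol. SAP Section 13, which records changes from the protocol, mentions visit windows only.

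**The concern.** A programmer following SAP Section 11.2 closes the window on the date of any surgery, whether or not the subject is still applying study drug. New or worsening events after that date are then not treatment-emergent, although the subject is exposed. A later serious event judged related to the drug would go to the listing of non-treatment-emergent SAEs and would be absent from the serious-TEAE and related-TEAE tables.

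This matters in Part 1 because the treated area grows over time, so the later weeks carry the largest exposure. Protocol Section 10 also makes the start of Part 2 depend on there being no safety impairment in Part 1. With about 9 subjects, one misplaced event is visible in every percentage.

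The 28-day end point raises a smaller question of the same kind: events that the protocol requires sites to collect on the last two days cannot be TEAEs.

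**Working it through.** The plan gives no figure of its own here. The check compares the definitions and then counts days.

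**Step 1: the two definitions**

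| Feature | Protocol 9.1.2 | SAP 11.2 |
|---|---|---|
| Start | After first dose | After first dose |
| Latest end | None beyond being in the study | Last dose + 28 days |
| Closed by surgery | No | Yes, unqualified |
| Closed by another investigational agent | No | Yes |
| Closed by rollover | No | Yes |

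**Step 2: does surgery end study treatment?** It is not among the investigator's withdrawal reasons in Protocol Section 4.3, nor among the prohibited therapies and procedures in Section 5.7.1. The protocol allows for procedures during the study. Section 9.1.1 explains how to record the condition behind a surgical procedure, and Section 9.1.3 exempts certain elective or preplanned hospital stays from SAE status. So surgery followed by continued dosing is possible.

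**Step 3: where excluded events would go.** They leave the TEAE tables listed in SAP Section 11.2. They stay in the by-patient AE listings, the row for at least one AE in the overall summary, and the listings of deaths and of non-treatment-emergent SAEs. SAP Section 11 and the opening part of 11.2 also plan tables of AEs as such. The all-AE listing carries an onset flag that labels anything on or after first dose as treatment, with no end date. An on-drug event after surgery would therefore have treatment onset by that flag and yet not be a TEAE.

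**Step 4: day counts for a subject who completes treatment.** Protocol Section 3.5 gives the duration: "This comprises of a 24-week study treatment phase followed by a 4-week follow-up period".

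- Treatment: 24 × 7 = 168 days.
- Collection after first dose: 168 + 30 = 198 days.
- Longest SAP window: 168 + 28 = 196 days.
- Gap: 198 − 196 = 2 days, which is 2/198 = 1.0% of days after first dose, or 2/30 = 6.7% of the collection period after last dose.

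**Step 5: surgery while on treatment.** The timing is an assumption, because the documents give none. The subject is assumed to go on to complete 24 weeks. Share of treatment days outside the window = (168 − 7 × week) / 168.

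| Assumed week of surgery | Treatment days outside the window | Share |
|---|---|---|
| 4 | 168 − 28 = 140 | 83% |
| 12 | 168 − 84 = 84 | 50% |
| 20 | 168 − 140 = 28 | 17% |

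Under Protocol Section 5.6, expansion to half the body starts at Week 13 and to the whole body at Week 21. Surgery at or before Week 12 thus puts the entire expanded-area period outside the window.

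**Step 6: effect of one subject.** The protocol synopsis plans 6 treated and 3 control subjects. One reclassified subject changes an incidence by 1/6 = 16.7 points on active or 1/3 = 33.3 points on vehicle.

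**The case against.** **The events are not lost.** A reader might infer that they vanish from the safety report, or that AE summaries show TEAEs only. The documents do not support that. The all-AE displays and listings in Step 3 remain, and the DSMB review in SAP Section 2.2 covers adverse events without restriction to TEAEs. This stands and limits the harm. It does not restore the tables of serious, related or discontinuation TEAEs. An all-AE count also mixes in events from before first dose. SAP Sections 11 and 11.2 are themselves not fully consistent on how many all-AE tables will be produced.

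**The on-treatment loss is conditional.** A reader might infer that on-treatment events are being dropped as a matter of course, or take 83% as the expected size. Neither follows. The SAP reports delayed blood draws and treatment interruptions, but no surgery, and neither document gives a frequency. The 83% belongs to one assumed date. This stands in full.

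**The phrase may mean an investigational procedure, or surgery after treatment.** Either reading is possible. The text says neither, and the earliest-date rule applies to it as written.

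**The 28-day limit is a convention that matches the follow-up period.** This largely stands. A reader might infer that two days are lost for every subject. They are not: for anyone who enters the extension within 28 days of the last dose, rollover has already closed the window.

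**The SAP covers Part 1 only and plans no inferential safety tests.** True. The concern is about descriptive counts, not a test result.

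**Conclusion.** The point holds as a defect in a definition, not as evidence that safety data are missing. SAP Section 11.2 departs from Protocol Section 9.1.2 without saying so in Section 13, and conflicts with its own onset flag. The surgical clause is the weightier part. Read literally, it can reclassify events in a subject who is still on study drug.

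Its size depends wholly on whether a subject has a procedure during treatment and continues dosing. If none does, the clause has no effect on on-treatment events. If one does, the share of treatment days outside the window runs from 17% to 83% over assumed dates from Week 20 back to Week 4. If that subject's only event of a given type falls after the procedure, the incidence changes by about 17 points on active or 33 on vehicle. The 28- versus 30-day mismatch is secondary: 2 of 198 days, and only for subjects who do not roll over earlier.

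The text should be corrected, because the rule as written is wrong for on-drug events and the change is small.

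**What to change.** In the TEAE definition in SAP Section 11.2:

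1. Delete the surgical-intervention cut-off. If the sponsor has a reason to keep it, reword it so that it cannot close the window while the subject is still on study drug.
2. Extend the end of the window from 28 to 30 days after the last dose, to match adverse event collection in Protocol Sections 6.5 and 9.
3. Keep the rollover cut-off, set at the first extension dose, and the investigational-agent cut-off only if both are declared in SAP Section 13 as departures from Protocol Section 9.1.2.
4. Check the onset flag in the all-AE listing against the revised definition.

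The cost is one sentence in Section 11.2, an entry in Section 13 and one changed derivation. No new data are needed, since events are already collected to 30 days. The downside for the sponsor is that TEAE counts may be slightly less favourable.
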